Appendix B: Included procedures

- Ileocolic resection
- Right hemicolectomy
- Extended right hemicolectomy
- Transverse colectomy
- Left hemicolectomy
- Sigmoid colectomy (including Hartmann's Procedure)
- Anterior resection
- Sub-total colectomy
- Total colectomy
- Pan-proctocolectomy
- Completion proctectomy
- Closure/reversal of stoma (ileostomy or colostomy)
- Formation of stoma (ileostomy or colostomy)

Appendix C: Clavien-Dindo classification system

Adverse post-operative events may be divided up into treatment failures, sequelae and complications.

- **Failure of treatment** occurs when the original surgery fails to achieve its intended benefits; for example, persistent pain following laparoscopic cholecystectomy or tumour recurrence following cancer surgery.
- **Sequelae** are the recognised consequences of a given procedure; for example, gut malabsorption following a large small bowel resection or immune deficiency following splenectomy.
- **Complication:** Any deviation from the normal post-operative course that has an adverse effect on the patient and is not either a treatment failure or sequel.

In the Clavien-Dindo classification (13), the factor determining the severity of a complication is the treatment required. Consequently, a given complication may be graded differently depending on how it has been managed. For example, an anastomotic leak may be managed just with antibiotics if it is contained (grade II) or it may require re-operation under anaesthetic (grade III).

Some other considerations:

Intra-operative complications are not considered unless they have an adverse effect on the patient post-operatively. The only exception to this is **intra-operative death**; this is classified as grade V.

All post-operative adverse events are included, even when there is no direct relationship to the surgery.

All adverse events within the follow-up period (30 days) are included, even if they occur following discharge.

Diagnostic procedures are not included. For example, a diagnostic oesophagoduodenoscopy (OGD) to look for a source of bleeding without any intervention would not be considered a complication, but a therapeutic OGD with clipping of a bleeding vessel would be considered a grade III complication. Since **negative exploratory laparotomies** are considered to be diagnostic procedures, they should not be recorded as complications.

Grade	Definition (examples listed in italics)
I	
Any deviation from the normal postoperative course without the need for pharmacological (other than the “allowed therapeutic regimens”), surgical, endoscopic or radiological intervention.
 
Allowed therapeutic regimens are: selected drugs (antiemetics, antipyretics, analgesics, diuretics and electrolyte replacement), physiotherapy and wound infections opened at the bedside but not treated with antibiotics.
 
Examples: Ileus (deviation from the norm); hypokalaemia treated with K; nausea treated with cyclizine; acute kidney injury treated with intravenous fluids.

II	
Requiring pharmacological treatment with drugs beyond those allowed for grade I complications. Blood transfusions and total parenteral nutrition are also included.
 
Examples: Surgical site infection treated with antibiotics; myocardial infarction treated medically; deep venous thrombosis treated with enoxaparin; pneumonia or urinary tract infection treated with antibiotics; blood transfusion for anaemia.

III	
Requiring surgical, endoscopic or radiological intervention
 
Examples: Therapeutic endoscopic therapy (do not include diagnostic procedures); interventional radiology procedure, return to theatre

IV	
Life-threatening complications requiring critical care management, neurological complications including brain haemorrhage and ischemic stroke (excluding TIA).
 
Examples: Single or multiple organ dysfunction requiring critical care management, e.g. pneumonia with ventilator support, renal failure with filtration; SAH; stroke.

V	
Death of a patient

Appendix D: Key steps successful centre inclusion

1. Contact your **local lead** about participation in the study at the centre of your choice. They will connect you to any other interested medical students and doctors at your centre.
2. Form a **mini-team of up to three collaborators**. If possible a **medical student** should coordinate the team and lead audit registration/data collection. They must be supported by at least one motivated doctor. This can be a doctor of any grade, but should preferably a junior doctor/ resident.
3. Choose a **14-day data collection period** within the data collection period to suit your availability. Multiple teams of students can participate at each centre, collecting data during distinct one-week periods. A single mini-team is permitted to collect data for more than one period if they have capacity.
4. Ensure that you secure **formal study approval** from your hospital according to local regulations.
 - This must be done prior to commencing data collection. UK collaborators should seek their NHS Trust's Caldicott Guardian's approval to upload data to REDCap. Non-UK collaborators should seek guidance from your national committee on your country's specific approval processes.
 - Ensure that your centre is aware that this study is **international** and data will be uploaded to **REDCap**. For more details on REDCap & data security see Section 12 of the study protocol. **No changes** to normal follow-up should be made.

It is essential that you begin this process immediately; approval can take up to 2-3 month. If you have any difficulties or are unsure what is required contact your local lead, your supervising surgeon, or your national network committee.

5. Once the audit is registered, please forward evidence of this to your national network committee. REDCap accounts will not be issued until proof of audit registration is received.
6. Arrange to **meet** with the other members of your mini-team, including the junior doctor/resident and, if possible, supervising consultant. If possible meet up with the **preceding mini-team** at your centre also. They will have a lot of helpful advice regarding what worked well. In your mini-team agree in advance who will be responsible for each stage of the project, e.g. identifying patients, collecting baseline data, completing follow-up, data entry to REDCap. Talk through how you will identify patients and collect required

data, it will be particularly helpful if the consultant is present to offer guidance regarding this.

7. **Identify all** patients meeting **inclusion criteria** within your 14-day period.

8. Regularly **follow-up** for information on complications over the **30-day post-operative period**. This study is a prospective study, so you should not wait until the end of the post-operative period to follow-up patients. Discuss the best way to follow up patients with the consultant supervising your audit, as this will vary from centre to centre.

9. Ensure all data has been uploaded to the **REDCap** system and you have completed all fields, avoiding **missing data points**. If more than 5% of patients at your centre are missing data, your centre cannot be included and your name will be withdrawn from the author list.

It is a **condition** of participation in the COMPASS study that following completion of the audit at your centre you **must** ensure that your **local results are presented** to your hospital's surgical department.

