Project team structure: Medical students will take the lead in disseminating and delivering this study alongside junior doctors. These ‘mini-teams’ should be supervised by a consultant surgeon at each site (Figure 1). Each team should include at least one qualified doctor to provide additional local support for participating medical students.

Training: The protocol was formally launched at the European Society of Coloproctology (ESCP) meeting on 26th September 2019. Investigators will be trained in the study background, design, and methodology. COMPASS regional and local leads are encouraged to hold local meetings with collaborating teams at their medical school to brief them on the protocol, and to feedback any local issues or questions raised. To ensure collaborators understand the study topic, drain follow-up, inclusion criteria, application of the Clavien-Dindo classification and the principles of data governance, they will all be asked to complete a series of online e-learning modules (pass mark is 100%) prior to starting data collection.

Data completeness: Following data collection, only data sets with >95% data completeness will be accepted for pooled analysis. To emphasise the importance of data completeness to collaborators, centres with >5% missing data points will be excluded from the study and collaborators from those centres withdrawn from the published list of citable collaborators.

Validation: Data validation will be performed at a minimum of five centres in each participating country. Data validators may be either a final year student or a qualified doctor who were not involved in the initial data collection.

The validator will be assigned a random 2-week data collection period at a local centre to validate. Data validation will occur following completion of data collection (including follow-up). After completing validation, the validator will send a summary of how many records were reviewed and error rates to the study management group. There are two components of validation:

I. Case ascertainment:

- The validator will independently identify all patients eligible for inclusion over the one 2-week study period. The target for data ascertainment is >95%.

II. Data collection

- The validator will independently collect data for the key data fields relating to risk-adjustment and outcome measures (see **Appendix A**).

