Criteria for centre inclusion within COMPASS:

- ▲ ● Successful completion of **at least one data collection period** at the centre (with a minimum of one eligible patient per period included). ▲
- Obtain all appropriate **local approvals** for conduct of the COMPASS audit.
- Individual data collection periods will only be included when:
 - I. >95% data completeness has been achieved.
 - II. Validation targets have been achieved (if performed).
 - III. All data for the period has been uploaded within the specified deadlines.

Please note if these criteria are not met, then the contributing mini-team and/or the centre may be removed from the dataset and authorship list (get in contact asap with potential issues arise so we can support your centre to be included). See Appendix D for advice to help ensure successful inclusion of your centre in the COMPASS audit.

16. Patient and Public Involvement

To better understand the role of drains in colorectal surgery and their impact on the post-operative period, we asked the opinion of patients, aiming to clarify what matters to them most in the post-operative period. Patients were invited to fill out an anonymous survey through social media. The main questions concerned their experience with drains in the post-operative period, with an emphasis on to which extent, in their opinion, the drain(s) facilitated / slowed down their recovery. Patients were also asked whether anyone discussed with them the possibility of placing a drain during surgery and to give their opinion regarding which are the most important outcomes a study focussed on surgical drains should explore.

Patients were concerned about possible post-operative complications and felt that their doctors placed a drain to prevent them. However, at the same time, they feared the drain might have slowed down their recovery as it caused severe pain and it significantly reduced their mobility and, therefore, independence. In light of their replies, we structured our study to capture the drain management practices of an international cohort of colorectal surgeons. We used the patients' insight to formulate a centre survey and case report form that will help us explore whether most surgeons adhere with the Enhanced Recovery After Surgery (ERAS) guidelines and, if not, understand their reasons for not being compliant.

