Intraoperative complications	None / Vascular injury / Bowel injury (e.g. duodenum) / Injury to other organs or structures (e.g. ureter)
Abdominal drain(s) inserted at time of surgery	Yes / No
Reason for drain identified	
Not identified Excessive intraoperative blood loss (or concern regarding this). Excessive intraoperative fluid (not blood) collections (or concern regarding this). Contaminated or dirty surgery

	
Positive air leak test (the intra-operative air leak test is a common intraoperative test used to identify mechanically insufficient anastomosis)
 
Poor vascularisation of the anastomosis (determined visually or by ICG fluorescence) (or concern regarding this).
 
Other reason identified (please specify)

Number of drains	Number
Type of drain(s) used	
Open (open drains drain fluid on to a gauze pad or into a stoma bag e.g. Penrose) / Close (tubes draining into a bag or bottle, e.g. Jackson-pratt).
 
Active (drains maintained under suction) / Passive (drains that have no suction and work according to the differential pressure between body cavities and the exterior).
 
(see REDCap for pictures)

Drain location	
Subcutaneous drain
 
Intraabdominal drain – pelvis
 
Intraabdominal drain – peritoneal cavity
 
Intraabdominal drain – posterior to the anastomosis
 
Intraabdominal drain – anterior to the anastomosis
 
Intraabdominal drain – near the anastomosis (not in contact)

Daily postoperative data points (to be completed for each inserted drain)	Required data (definition / comment)
Day of surgery is defined as Post-operative Day (POD) 0. The day after surgery is therefore defined as POD 1 and day 10 after surgery as POD 10.	
Volume drained (Daily POD 1-10)	
Millilitres (recordings of drain output must correspond to the entire day, i.e. 8am to 8am).
 
It is recommended that you collect data one day in retrospect.

Contents of drain output (Daily POD 1-10)	
Serous fluid (with or without blood staining) / Frank blood / Purulent / Faecal
 
(see REDCap for pictures)

Drain-related data points	Required data (definition / comment)

Day of drain removal	Post-operative Day (POD)
Surgical site infection	Yes – Site of Drain(s) / Yes – Other incision / No As defined by US Centers for Disease Control and Prevention (CDC)

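### The data-completeness rule is stated in three ways, and the patient-count version in Appendix D excludes an average-sized centre for one incomplete patient

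*Protocol*

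**What the plan says.** The protocol states the completeness condition in three places.

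- **Section 14, Data completeness.** The unit is the data point and the body excluded is the centre: "centres with >5% missing data points will be excluded from the study". The same paragraph says that "only data sets with >95% data completeness will be accepted for pooled analysis", without defining a data set.
- **Section 15, Criteria for centre inclusion.** The unit is the 14-day period: "Individual data collection periods will only be included when" three conditions are met, the first being ">95% data completeness has been achieved". The text that follows makes removal of the mini-team or centre a possibility, not a certainty.
- **Appendix D, step 9.** The unit is the patient and the body excluded is the centre: "If more than 5% of patients at your centre are missing data, your centre cannot be included".

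Section 15 also makes the validation targets a condition for including a period, but only where validation was done. Section 14 sets the case-ascertainment target above 95%, judged over one two-week period.

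**The concern.** These rules decide which centres and periods enter the dataset. If they disagree, the analysed population depends on which sentence is applied, and that choice could be made after the data have been seen.

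A 5% tolerance also behaves differently on different counts. Over hundreds of data points it leaves room for ordinary gaps. Over 6 or 17 patients it leaves none, so a centre with almost complete data can be lost.

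The primary outcome is whether a drain was placed, and a drained patient has more fields to complete. A rule that penalises any incomplete patient could therefore act unevenly on drained and undrained patients.

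**Working it through.** **Inputs from the protocol**
- Section 11: 3 patients per week per centre, 300 centres (150 + 150), about 5000 patients.
- Sections 2 and 4: 14-day periods.
- Sections 14 and 15 and Appendix D: the thresholds above.

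**Assumptions**
- About 41 fields apply to every patient, by a count of Appendix A. A patient with one drain removed near day 5 has about 21 more, so 62.
- The protocol gives no missing rate m, so a range is shown. Fields are taken as missing independently.

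**Volumes**
- Per period: 3 × 2 = 6 patients.
- Planned total: 300 × 6 = 1800 for each period that every centre runs. Two periods give 3600 and three give 5400. The planned 5000 lies between them (5000/1800 = 2.78 periods per centre). The number of periods per centre is not stated, so the 5000 is not shown to be wrong.
- Per centre: 5000/300 = 16.7, or about 17 patients.

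**The same data under two rules.** Take 17 patients × 41 fields = 697 data points with one missing. Missing data points are 1/697 = 0.14%, which passes section 14. Incomplete patients are 1/17 = 5.9%, which fails Appendix D.

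**Patient rule, smallest workable centre.** One incomplete patient is 1/6 = 16.7%, 1/17 = 5.9%, 1/19 = 5.3% or 1/20 = 5.0%. At least 20 patients are needed before one incomplete patient passes.

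**Patient rule, probability of exclusion.** Below 20 patients this is 1 − (1 − m)^(41n) when no patient is drained. For n = 6 and m = 0.5%: 1 − 0.995^246 = 71%. At n = 24 one incomplete patient is allowed, so the binomial tail is used.

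| m | n = 6 | n = 17 | n = 24 |
|---|---|---|---|
| 0.1% | 22% | 50% | 25% |
| 0.5% | 71% | 97% | 95% |
| 1% | 92% | >99% | >99% |

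**Data-point rule, for comparison.** A 6-patient period has 6 × 41 = 246 points and fails when 13 or more are missing. The binomial tail is below 0.1% at m = 1%, 0.15% at 2%, 3.6% at 3% and 19% at 4%.

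**Drains under the patient rule.** With six patients and equal missing rates, compare none drained (246 fields) with all drained (6 × 62 = 372 fields). Failure is 22% against 31% at m = 0.1%, 71% against 85% at 0.5%, and 92% against 98% at 1%.

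**Drains under the data-point rule.** With six patients, none against all drained:
- 3% missing everywhere: 3.6% against 1.8%, the reverse direction.
- 2% in general fields and 5% in drain fields: 0.2% against 1.9%.
- 2% in general fields and 10% in drain fields: 0.2% against 39%.

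**Ascertainment.** 19/20 = 95.0% is not above 95%, while 20/21 = 95.2% is. So 21 eligible patients are needed before one may be missed. With 6 eligible, failure is 1 − p^6: 17% at true ascertainment p = 97%, 11% at 98% and 6% at 99%.

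**The case against.** The best defence is that there is one clear conflict, not three. Sections 14 and 15 can operate as nested conditions on the same measure, first by period and then by centre. Section 15 presents Appendix D as advice, and the sentence in step 9 just before the patient rule itself speaks of data points, so the patient wording may be a loose paraphrase. Section 15 also leaves removal to discretion and invites centres to raise problems early. All of this is fair. It does not cure the conflict, because step 9 is worded as an absolute bar that also removes names from the author list, and a collaborator following it would reach a different result from section 14.

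A reader might go further and infer any of the following. The document does not support them.

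- **That every threshold discards sound periods.** The data-point rule does so at most 0.15% of the time at 1–2% missing.
- **That the Appendix D rule applies to each period.** It is worded per centre. The 6-patient column holds for a centre running a single period.
- **That exclusion under the data-point rule rises with drain use and biases adherence upward.** This needs drain fields to be missing more often than the rest. Daily drain-chart collection makes that plausible, but the protocol gives no rate, and at equal rates the direction reverses.
- **That removing failed validated periods makes reported quality near-perfect.** Validators report records reviewed and error rates to the study management group. Nothing says the published figures are calculated after removals.

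**Conclusion.** The point holds as a contradiction and a small-denominator problem. Appendix D, step 9 conflicts with section 14, and at about 17 patients per centre it amounts to a demand for perfect data. It would exclude half of such centres at 0.1% missing fields and nearly all at 0.5%. These figures rest on the count of about 41 fields, independent missingness and no drained patients; drained patients raise them. The thresholds of 20 and 21 patients rest on no assumption.

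Selection by drain use follows from the patient rule through form length alone, and is modest (71% against 85% at 0.5% missing, for the extreme contrast of none against all drained). Under the data-point rule it is a conditional risk only.

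The ascertainment problem is real but is confined to periods that are validated, so teams of equal quality are treated differently according to whether a validator reached them.

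This should be corrected. It does not show that the planned primary result is biased. A statistical analysis plan, not seen here, may settle which rule is used, but the protocol's own sentences would still disagree.

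**What to change.** 1. Delete the patient-based sentence in Appendix D, step 9. State one rule identically in section 14, section 15 and Appendix D: more than 95% of applicable data points, with one named unit (centre or centre-period) and one consequence, either mandatory or discretionary. Fix this before the data are examined.
2. Judge the case-ascertainment target on the pooled validated sample, instead of deleting single small validated periods.
3. As a sensitivity analysis, report the primary outcome in all approved periods where drain placement (yes or no) is recorded, whether or not the period met the completeness rule.

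Daily drain output need not be exempted from the completeness count. It is part of a secondary outcome, and leaving it out would be a matter of preference.

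The cost is protocol wording and one extra analysis. The downside is that slightly more missing data is retained.
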